3 INTRODUCTION

This SAP has been developed to supplement the statistical analyses described in the clinical study protocol version 2.0 dated 18 May 2015.

This SAP describes the methodology and considerations of the planned analyses and a list of all the TFLs for this study. A detailed description of the planned TFLs will be provided in a separate TFL shells document. Any changes to the TFL shells numbering or to the title of the TFLs will not require an amendment to this SAP.

This SAP and any amendments will be finalized prior to the lock of the clinical database. Any changes to the analyses described in this document or additional analyses performed to supplement the planned analyses, will be described in the clinical study report (CSR).

The preparation of this SAP is based on the following documents:

- International Conference on Harmonisation (ICH) E9 guideline entitled, “Guidance for Industry: Statistical Principles for Clinical Trials” (**ICH Guideline E9, 1998**).
- ICH E3 guideline entitled, “Guidance for Industry: Structure and Content of Clinical Study Reports” (**ICH Guideline E3, 1995**).
- The Committee for Medicinal Products for Human Use (CHMP) Guideline on the Investigation of Bioequivalence (**CHMP, 2010**).
- The Appendix IV of the CHMP Guideline on the Investigation on Bioequivalence (**CHMP Appendix IV, 2011**).
- Food and Drug Administration (FDA) Guidance to Industry for Statistical Approaches to Establishing Bioequivalence (**FDA, 2001**).
- Electronic case report forms (eCRF) Version 4.0 dated 04 May 2015.
- Biostatistical Addendum – Subject Randomization List version 2.0 (16 June 2015).

3.1 Revision History

Version	Date of Revision	Revision
1.0	17 November 2015	Final 1

4 ABBREVIATIONS AND DEFINITION OF TERMS

The following abbreviations are used within this SAP.

%AUC _{extr}	Percentage of AUC that is extrapolated from t _{last} to infinity
ADL	Activities of daily living
AE	Adverse event
ANOVA	Analysis of variance
ATC	Anatomical Therapeutic and Chemical
AUC	Area under the concentration-time curve
AUC _(0-∞)	Area under the concentration-time curve from T ₀ extrapolated to infinity
AUC _(0-last)	Area under the concentration-time curve from T ₀ to time of last quantifiable concentration
AUC _(0-t')	Partial AUC, where t' is the subject-specific time of maximum nicotine concentration following the single use of cigarettes or nicotine nasal spray
BLQ	Below the Lower limit of Quantification
BMI	Body mass index
CC	Conventional cigarette(s)
CD	Compact disc
CI	Confidence interval
C _{last}	Last quantifiable concentration
C _{max}	Maximum concentration
CC	Conventional Cigarette
CH	Cigarette Holder
CHTP	Carbon Heated Tobacco Product
CHMP	Committee for Medicinal Products for Human Use
CI	Confidence Interval
C _{last}	The last quantifiable concentration
C _{max}	Maximum observed plasma concentration.
CO	Carbon monoxide
COHb	Carboxyhemoglobin
COT	Cotinine
CRF	Case report form
CRO	Contract research organization
CSR	Clinical study report
CTCAE	Common terminology criteria for adverse events and common toxicity criteria
CTMS	Clinical trial management system
CV	Coefficient of variation
CYP2A6	Cytochrome P450 2A6

DDE	Drug Dictionary Enhanced
ECG	Electrocardiogram
eCRF	Electronic Case Report Form
EOS	End of study
FDA	Food and Drug Administration
FEV ₁	Forced expiratory volume in 1 second
FTND	Fagerström test for nicotine dependence (revised version)
FVC	Forced vital capacity
GCP	Good Clinical Practice
HCOT	Trans-3'hydroxycotine
HIV	Human immunodeficiency virus
HPHCs	Harmful and potentially harmful constituents
IB	Investigator's Brochure
ICF	Informed consent form
ICH	International Conference on Harmonization
IP	Investigational product
IRB	Institutional Review Board
ISO	International Organization for Standardization
IV	Intravenous
IxRS	Interactive web/voice response system
LLN	Lower limit of the normal range
LLOQ	Lower limit of quantification
LS	Least Squares
mCC	Menthol conventional cigarette
MCEQ	Modified cigarette evaluation questionnaire
MedDRA	Medical dictionary for regulatory activities
M RTP	Modified risk tobacco product
MSE	Mean square error of the fitted model residual
NR	No Result
PK	Pharmacokinetic(s)
PMI	Philip Morris International
PT	Preferred Term
QC	Quality control
QSU-brief	Questionnaire of smoking urges
QTcB	QT Interval Corrected using Bazett's Formula
QTcF	QT Interval Corrected using Fridericia's Formula
REML	Restricted Maximum Likelihood
SAE	Serious adverse event
SAP	Statistical analysis plan
SD	Standard Deviation
SHM	Sample handling manual
SOC	System Organ Class
SOP	Standard operating procedure
T	Time point

t'	Subject-specific time of maximum nicotine concentration following single use of mCC or CHTP 1.1 M product
T_0	Time point of first product use during study day
$t_{1/2}$	Half-life
t_{last}	Time of last quantifiable concentration
t_{max}	Time to maximum concentration
TFL	Tables, Figures, and Listings
UBC	United BioSource Corporation
ULN	Upper limit of the normal range
ULOQ	Upper limit of quantification
VAS	Visual analogue scale
WBC	White blood cell (count)
WHO	World Health Organization
λ_z	Terminal elimination rate constant

The following special terms are used in this SAP:

End of Study	date when the subject completes his/her 7-day safety follow-up period
First product use time point	Start of the product test use.
mCC	The term 'menthol conventional cigarette' refers to manufactured and commercially available menthol cigarettes and excludes hand-rolled cigarettes, cigars, pipes, bidis, and other nicotine-containing products.
Carbon Heated Tobacco Product 1.1 Menthol (CHTP 1.1 M)	CHTP 1.1 M is a tobacco stick which is comparable in shape and form, and is used in a similar manner to a menthol conventional cigarette. To use the CHTP 1.1 M, the consumer removes the protective cap and uses a conventional lighting method to ignite the heat source. [REDACTED], the aerosol generated by the heating process is inhaled by placing the lips on the filter and drawing air through the CHTP 1.1 M.
Randomization	Assignment to the respective product at any time on Day -1 utilizing an interactive web and voice response system (IxRS). On Day 1, the subjects will be individually informed about the product they are randomized to just before the first product use.
Screen failure	Subject who signs informed consent form but does not meet

the entry criteria prior to enrolment at Admission (Day -3) or met all entry criteria, but was not enrolled due to completion of enrolment (*i.e.*, supernumerary subject). Re-screening of subjects who did not meet any entry criteria will not be permitted.

5 STUDY OBJECTIVES AND ENDPOINTS

5.1 Primary Objective and Endpoints

1. To evaluate the rate and amount of nicotine absorbed (as assessed by maximum plasma concentration [C_{\max}] and area under the concentration-time curve [AUC] from start of product use to time of last quantifiable concentration [$AUC_{(0-\text{last})}$]) from the CHTP 1.1 M relative to mCC following single use of the CHTP 1.1 M and mCC.

Endpoints:

- C_{\max}
- $AUC_{(0-\text{last})}$

5.2 Secondary Objectives and Endpoints

1. To evaluate the difference on nicotine pharmacokinetic (PK) absorption parameters (AUC from start of product use extrapolated to infinity [$AUC_{(0-\infty)}$], up to 12 hours [$AUC_{(0-12)}$], and partial $AUC_{(0-t')}$, where t' is the subject-specific time of maximum nicotine concentration following single use of the mCC [$AUC_{(0-t')}$]) between the CHTP 1.1 M and mCC.

Endpoints:

- $AUC_{(0-\infty)}$
- $AUC_{(0-12)}$
- Partial $AUC_{(0-t')}$

2. To evaluate the time to the maximum concentration (t_{\max}) of nicotine for the CHTP 1.1 M as compared to mCC.

Endpoint:

- t_{\max}

3. To describe the terminal half-life ($t_{1/2}$) of plasma nicotine for the CHTP 1.1 M and mCC.

Endpoint:

- $t_{1/2}$

4. To describe the differences on urge-to-smoke over time between the CHTP 1.1 M and mCC.

Endpoint:

- Urge-to-smoke questionnaire (questionnaire of smoking urges brief [QSU-brief]) total score, factor 1 and factor 2

5. To describe product evaluation of the CHTP 1.1 M and mCC.

Endpoint:

- Product evaluation questionnaire (modified cigarette evaluation questionnaire [MCEQ]) subscales scores
6. To describe the levels of carbon monoxide (CO) exposure for the CHTP 1.1 M as compared to mCC.
Endpoint:
- CO exposure biomarkers: levels of exhaled CO and carboxyhemoglobin (COHb) in blood
7. To monitor the safety during the study.
Endpoints:
- Incidence of adverse events (AEs)/serious adverse events (SAEs)
 - Respiratory symptoms: cough assessment by visual analogue and Likert scales and one open question
 - Vital signs
 - Spirometry
 - Electrocardiogram (ECG)
 - Clinical chemistry, hematology, and urine analysis safety panel
 - Physical examination
 - Concomitant medication.
 - Incidence of CHTP 1.1 M malfunctions and misuse. [REDACTED]

5.3 Additional Endpoints

The following additional assessments (for baseline characteristics) will be made:

- Serology for human immunodeficiency virus 1/2 and hepatitis B and C
- Urine pregnancy test (female subjects of childbearing potential only), urine cotinine test, urine drug screen
- Alcohol breath test
- Chest X-ray
- Nicotine dependence to be assessed with the Fagerström test for nicotine dependence revised version
- Cytochrome P450 2A6 (CYP2A6) activity expressed as *trans*-3'-hydroxycotinine/cotinine molar metabolite ratio in plasma

5.4 Study Hypotheses And Evaluation Criteria

5.4.1 Hypotheses

Given that the objective of this study is to determine the point estimate and precision of the ratio of the CHTP 1.1 M:mCC for C_{\max} and $AUC_{0-\text{last}}$, there is no statistical hypothesis to be tested.

5.4.2 Evaluation Criteria

The study will target to describe the 95% confidence intervals (CI) of the CHTP 1.1 M:mCC ratio for the primary nicotine PK parameters estimated with a precision of $\pm 30\%$.

6 INVESTIGATIONAL PLAN

6.1 Study Design

[figure not shown]
This is a randomized, controlled, 2-period, 2-sequence, single-use crossover study. Each subject will receive CHTP 1.1 M and mCC (Figure 1 Study Flow Chart).

The end of the study is defined as the date when the last subject completes his/her 7-day safety follow-up period.

Subjects that terminate the study after Enrolment and prior to completion of the study will be asked to undertake early termination procedures.

1) Screening and Admission (from the ICF Signature to the Enrolment at Admission):

A Screening Visit will be conducted within 4 weeks (Day -31 to Day -4) prior to Admission to the investigational site (Day -3). A demonstration of the CHTP 1.1 M will be done by the site collaborators during the Screening Visit. Screening procedures do not necessarily have to be conducted on the same day. On Day -3 (Admission), after all inclusion/exclusion criteria are checked, all eligible subjects will be enrolled and perform a product test using 3 to 5 CHTPs 1.1 M. After product test, subjects not ready to use the CHTP 1.1 M will be discontinued. All subjects that are not enrolled are considered as screen failures. Subject will be instructed not to smoke in the morning prior to Admission. After Admission, smoking will not be allowed until blood drawing for the assessment of CYP2A6 activity and spirometry have been performed (Section 9.2). After these assessment procedures, smoking will be allowed until 11.00 PM at Admission.

**Figure 1 Study Flow Chart****2) The Investigational Period (from Day -2 to Discharge):**

The Investigational period will consist of 2 periods (Period 1, Period 2) with each period consisting of approximately 48 to 57 hours smoking abstinence and 1 day of single product use.

Period 1: From Day -2 to Day 1. After Day 1 product use, the subject will start his/her washout for period 2

Period 2: From Day 2 to Day 3. The products should be used at the same time (within 1 hour) on Day 1 and Day 3

48 eligible, healthy smoking subjects will be randomized to one of 2 sequences:

Table 1 Definition of Randomization Sequences

Sequence	Sample Size
1. CHTP 1.1 M then mCC	24
2. mCC then CHTP 1.1 M	24

Each sex and smoking strata (International Organization for Standardization [ISO] nicotine levels ≤ 0.6 mg vs. >0.6 to 1.0 mg) will have a quota applied to ensure they represent at least 40% of the study population for each Sequence (Sequence 1 and Sequence 2).

Subjects who do not complete the study after randomization will not be replaced.

Subjects will be discharged from the investigational site in the morning of Day 4 after performance of Discharge assessments.

3) The Safety Follow-up Period (from Discharge until Day 11):

A 7-day safety follow-up will be done for the recording of spontaneously reported AEs and SAEs (passive surveillance) and the active follow-up by the investigational site of AEs/SAEs ongoing at Discharge. Any AE will in general be followed-up until resolved, stabilized (*i.e.*, no worsening of the event), or until a plausible explanation for the event has been found.

The end of study for the subject is defined as the date of completion or discontinuation on Subject status form completed. AEs/SAEs not resolved or not stabilized at EOS are to be recorded as ongoing at EOS.

6.2 Selection of Study Population

6.2.1 Inclusion Criteria

Subjects who meet all the following inclusion criteria can be enrolled into the study:

1. Subject has signed the ICF and is able to understand the information provided in the ICF.
2. Subject is at a minimum 23 years of age (inclusive) at Screening.
3. Subject is Japanese.
4. Currently smoking, healthy subject as judged by the Investigator or designee based on assessments from the Screening period (*e.g.*, safety laboratory, spirometry, vital signs, physical examination, ECG, and medical history, X-ray).
5. Subject smokes at least 10 commercially available mCCs per day for the last 4 weeks prior to Screening and Admission, based on self-reporting (no brand restriction). Furthermore, the subject has been smoking for at least the last 3 consecutive years. The smoking status will be verified based on a urinary cotinine test (cotinine \geq 200 ng/mL).
6. The subject does not plan to quit smoking in the next 3 months.
7. The subject is ready to accept interruptions of smoking for up to 6 days.
8. The subject is ready to accept using the CTHP 1.1 M.

6.2.2 Exclusion Criteria

Subjects who meet any of the following exclusion criteria must not be enrolled into the study:

1. As per the Investigator's judgment, the subject cannot participate in the study for any reason (*e.g.*, medical, psychiatric, and/or social reason).
2. A subject who is legally incompetent, or physically or mentally incapable of giving consent (*e.g.*, emergency situation, under guardianship, subject in a social or sanitary establishment, prisoners, or subjects who are involuntarily incarcerated).
3. The subject has a clinically relevant disease which requires medication (including but not limited to gastrointestinal, renal, hepatic, neurological, hematological, endocrine, oncological, urological, immunological, pulmonary, and cardiovascular disease or any other medical condition (including safety laboratory as per CTCAE), which as per the judgment of the Investigator or designee would jeopardize the safety of the subject.
4. The subject has $(FEV_1/FVC) < 0.7$ and $FEV_1 < 80\%$ predicted value at post-bronchodilator spirometry.
5. The subject has asthma condition ($FEV_1/FVC < 0.75$ and reversibility in $FEV_1 > 12\%$ (or > 200 mL) from pre- to post-bronchodilator values).
6. The subject has a body mass index (BMI) < 18.5 or ≥ 32.0 kg/m².
7. As per the Investigator's judgment, the subject has medical conditions which require or will require in the course of the study, a medical intervention (*e.g.*, start of treatment, surgery, hospitalization) which may interfere with the study participation and/or study results.
8. The subject has used nicotine-containing products other than commercially available mCC (either tobacco-based products or nicotine replacement therapies), as well as electronic cigarettes and similar devices, within 4 weeks prior to assessment.
9. The subject has received medication (prescription or over-the-counter) within 14 days or within 5 half-lives of the drug prior to Admission (whichever is longer) which has an impact on CYP2A6 activity.
10. The subject has a positive alcohol test and/or the subject has a history of alcohol abuse that could interfere with the subject's participation in study.
11. The subject has a positive urine drug test.
12. The subject has a positive serology test for HIV 1/2, Hepatitis B, or Hepatitis C.
13. Donation or receipt of whole blood or blood products within 3 months prior to Admission.
14. The subject is a current or former employee of the tobacco industry or of their first-degree relatives (parent, sibling, child).
15. The subject is an employee of the investigational site or any other parties involved in the study or of their first-degree relatives (parent, sibling, child).
16. The subject has participated in a clinical study within 3 months prior to the Screening Visit.
17. The subject has been previously screened in this study and failed to meet the eligibility criteria.
18. For women of childbearing potential only: Subject is pregnant (does not have negative pregnancy tests at Screening and at Admission if not post-menopausal) or is breast feeding.

19. For women of childbearing potential only: Subject does not agree to use an acceptable method of effective contraception: intrauterine device, intrauterine system, barrier methods of contraception (condoms, occlusive caps) with spermicidal foam/gel/film/suppository, hormonal contraception containing progesterone only, vasectomized partner(s), or true abstinence (periodic abstinence and withdrawal are not effective methods) from Screening until the end of the safety follow-up period. Hormonal contraception with estrogen containing products is NOT allowed in this study.

6.3 Product Allocation and Blinding

6.3.1 Methods of Assigning Subjects to Treatment Sequences

Randomization to product exposure sequence will be done through [REDACTED].

Each sex and each of the smoking level (ISO nicotine levels ≤ 0.6 mg and >0.6 to 1 mg) will have a quota applied to ensure they represent at least 40% of the total study.

In particular, the maximum number of subjects having the same sex or nicotine level value will be limited to 28.

The randomization of the planned sample size of 48 subjects will be ensured by applying quota to the number of subjects per each sequence (24 subjects).

Subjects will be randomly assigned to one of the two product exposure sequences by means of a permuted-block schema. Block size and other randomization details will be available in the randomization plan.

The randomization plan will be generated by an independent statistician and none of the CRO and sponsor staff, Investigators, and study subjects will have any access to the randomization schema prior to randomization.

6.3.2 Blinding

This is an open-label study; therefore the subjects and Investigators or designee will be unblinded to the subject's sequence. However, there will be a limited degree of blinding in the data review and data analysis process. In particular, PMI and CRO personnel will be blinded to the randomized sequence as summarized in Table 2:

**Table 2 Description of Blinded Study Personnel**

Blinded Study Personnel	End of Blinding Period
PMI and CRO study statisticians	After the SAP finalization or database lock ¹ , whichever comes last
PMI clinical scientist	After the finalization of PMI blind database review ² . Can be actively un-blinded when appropriate.

¹ Data will be accessible blinded to randomization sequence and to product use by means of a dummy randomization or masking.

² As part of the PMI quality control (QC) activity, data listings will be reviewed by the CRO and PMI before database lock, with no access to the randomization information. Full details will be available in the data review plan.

Any PMI and CRO personnel who are not listed in the above table will be unblinded by default.

6.3.3 Compliance to Product Allocation

Compliance for all sequences will be ensured by strict distribution of the products (product by product) and collection of used CHTP 1.1 M and the mCC butts after use will be documented in appropriate logs.

The CO breath test will be considered as one of the measures of compliance during the wash-out days in all subjects.

7 DERIVED AND COMPUTED VARIABLES

Mean change from baseline is the mean of all individual subjects' change from baseline values (baseline is defined in Section 11.1.4 "Definitions for Statistical Data Analysis"). Each individual change from baseline will be calculated by subtracting the individual subject's baseline value from the value at the timepoint. The individual subject's change from baseline values will be used to calculate the mean change from baseline.

Reported BMI will be calculated from the body weight and height using the following formula:

$$\text{BMI} = \frac{\text{weight in kilograms}}{\text{height in meters}^2} \quad (\text{kg/m}^2)$$

The QT interval corrected using Fridericia's formula (QTcF) will be calculated as follows:

$$QTcF = \frac{QT}{\sqrt[3]{(60/HR)}}$$

The QT interval corrected using Bazett's formula (QTcB) will be calculated as follows:

$$QTcB = \frac{QT}{\sqrt{(60/HR)}}$$

The geometric coefficient of variation (CV) will be calculated using the following formula:

$$CV = 100\sqrt{e^{\text{var}} - 1}$$

where var = the variance from the log transformed data.

7.1 Pharmacokinetic Parameters

The following PK parameters will be determined from the plasma concentration-time profiles of nicotine using non-compartmental procedures in WinNonlin Phoenix, Version 6.2, or higher:

**Table 3: Definition of PK Parameters**

Parameter	Definition
$AUC_{(0-last)}$	Area under the plasma concentration-time curve from start of product use to the time of the last quantifiable concentration.
$AUC_{(0-t')}$	Area under the plasma concentration-time curve from start of product use to the subject-specific time (t') of maximum nicotine concentration following single use of mCC or CHTP 1.1 M product.
$AUC_{(0-12)}$	Area under the plasma concentration-time curve from start of product use to the 12 hours time point.
$AUC_{(0-\infty)}$	Area under the plasma concentration-time curve from start of product use extrapolated to infinite time.
$\%AUC_{extrap}$	Percentage of AUC that is extrapolated from t_{last} to infinity.
C_{max}	Maximum observed plasma concentration.
C_{last}	Last quantifiable concentration.
t_{last}	Time of the last quantifiable concentration.
t_{max}	Time of maximum observed plasma concentration.
λ_z	Terminal elimination rate constant, estimated by linear regression analysis of the natural log-transformed concentration-time data.
$t_{1/2}$	Terminal elimination half-life.

Additional PK parameters may be determined in order to support the interpretation where appropriate.

The actual blood sampling times post-exposure collected in the eCRF will be used in the computation of the PK parameters, with the exception of pre-exposure (-15 mins) blood sampling time which will be considered as time zero (T_0).

7.1.1 Calculation of C_{max} and t_{max}

The minimum requirement for the determination of the C_{max} is the inclusion of at least one quantifiable concentration within 1 hour post-exposure.

C_{max} and t_{max} will be obtained directly from the plasma concentration-time profiles. If C_{max} occurs at more than one time point, t_{max} will be assigned to the first occurrence of the C_{max} .

7.1.2 Calculation of AUC

The minimum requirement for the calculation of the AUC is the inclusion of at least 3 consecutive plasma concentrations above the lower limit of quantification (LLOQ), with at least 1 of these concentrations following C_{max} .

$AUC_{(0-last)}$, $AUC_{(0-12)}$ and $AUC_{(0-t')}$ will be calculated using the linear trapezoidal method.

$AUC_{(0-t')}$ will be calculated by linear interpolation within WinNonlin, where t' is the subject-specific actual time of maximum nicotine concentration following single use of mCC or CHTP 1.1 M.

$AUC_{(0-\infty)}$ will be calculated as follows:

$$AUC_{0-\infty} = AUC_{0-last} + \left(\frac{C_{last}}{\lambda_z} \right)$$

Where C_{last} is the last quantifiable concentration and λ_z is the terminal elimination rate constant.

$\%AUC_{extrap}$, the percentage of $AUC_{(0-\infty)}$ extrapolated beyond t_{last} , will be calculated according to the following formula:

$$\%AUC_{extrap} = \left(1 - \frac{AUC_{0-last}}{AUC_{0-\infty}} \right) \times 100$$

$AUC_{(0-\infty)}$ values where the percentage extrapolation is greater than 20% will be flagged in the data listings and will be reviewed for inclusion in the analysis during the pre-analysis data review.

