11.1.5 Handling of Dropouts or Missing Data (including outside the limits of quantification)

For questionnaire data total scores and domain or subscale scores may use a certain degree of imputation (by averaging across individual item scores) as detailed in Section 7.3 “Questionnaires”.

In general, values below the lower limit of quantification (LLOQ) will be imputed using 0.5 x lower limit of quantification. For values above the upper limit of quantification (ULOQ), *i.e.*, preceded by a “>”, for example “>xx,” the numerical xx will be used for calculation and reporting in summary tables. The number and percent of values below LLOQ or above ULOQ will be presented in each summary table.

For the calculation of PK parameters, partial dates/times for PK assessments or T_0 will not in general be imputed. For time points recorded in the format hh:mm, instead of hh:mm:ss, the missing information on seconds will be imputed by 30 sec.

For PK concentration data:

- 1) Where there is a missing sample taken at 1 h post-exposure or later
 - and in the subsequent PK sample, nicotine is quantifiable the data will be analysed and reported as planned.
 - And in the subsequent PK sample, nicotine is not quantifiable (BQL) or the missing sample result occurs at 24 h post-exposure AUC_{0-last} will, as well as being analysed and reported as planned, have a sensitivity analysis excluding those subjects.
- 2) Where there is a missing sample before 1 h post-exposure the parameters C_{max} and t_{max} will, as well as being analysed and reported as planned, have a sensitivity analysis excluding those subjects who have a missing sample before 1 h post-exposure.
- 3) Where the sample for the 15 min < T_0 time point is missing AUC_{0-t} will, as well as being analysed and reported as planned, have a sensitivity analysis excluding those subjects who have a missing sample at the 15 min < T_0 time point.
- 4) Where a subject was withdrawn at the 1 h post-exposure or later sample time, the only parameters to be reported would be C_{max} , t_{max} and AUC_{0-t} . All other parameters would be presented as NC (Not calculated) since only a limited partial concentration-

time profile is available and it is not comparable with the same parameters calculated for the other subjects and products and would therefore not be included in the statistical analysis.

- 5) If a subject is withdrawn < 1 h post-exposure, all PK parameters will be presented as NC.

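### The cut-off t' for the secondary endpoint AUC(0-t') is the mCC tmax in Section 5.2, but elsewhere is "of maximum nicotine concentration following single use of mCC or CHTP 1.1 M product", with no reference product named

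*SAP*

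**What the plan says.** - **Section 5.2, objective 1:** t' "is the subject-specific time of maximum nicotine concentration following single use of the mCC". One reference product is named.
- **Section 4, entry t':** "Subject-specific time of maximum nicotine concentration following single use of mCC or CHTP 1.1 M product".
- **Table 3, entry AUC(0-t'):** the time "of maximum nicotine concentration following single use of mCC or CHTP 1.1 M product".
- **Section 7.1.2:** t' is "the subject-specific actual time of maximum nicotine concentration following single use of mCC or CHTP 1.1 M", and AUC(0-t') "will be calculated by linear interpolation within WinNonlin".
- **Section 4, entry AUC(0-t'):** "the subject-specific time of maximum nicotine concentration following the single use of cigarettes or nicotine nasal spray". No nasal spray is used in this trial.
- **Section 7.1.1:** Cmax and tmax "will be obtained directly from the plasma concentration-time profiles".
- **Section 11.1.5, item 4:** the rule opens "Where a subject was withdrawn at the 1 h post-exposure or later sample time, the only parameters to be reported would be". Three parameters follow: the peak concentration, its time, and one printed as AUC0-t, apparently AUC(0-t') without its prime.
- **Section 11.6.2.1:** AUC(0-t') is log-transformed and analysed with the primary ANOVA model, in subjects with evaluable data on both products.

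Section 9, which lists changes from the protocol's analysis, does not mention t'.

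**The concern.** Each subject uses both products, so a completing subject has a tmax for each. Section 5.2 says which one sets the window; the passages a PK programmer would work from do not. Three readings are open: the mCC tmax for both profiles, the CHTP 1.1 M tmax for both profiles, or each product's own tmax.

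These are different estimands. The first two compare the products over a common early window, of different length. The third compares them over different windows, so a product that peaks later accumulates area for longer and slower absorption can look like greater early exposure. AUC(0-t') is a named secondary endpoint in a study whose stated aim is estimation, so the definition should be settled before anyone sees results by product.

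**Working it through.** **Step 1: can the text settle it?**

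- For a common cut-off: Section 7.1.2 calls for linear interpolation. A product's own tmax is already one of its observed sample times (Section 7.1.1), so interpolation is needed only when a time from one profile is applied to the other. This still does not say whose tmax is used.
- For an own-product cut-off: item 4 of Section 11.1.5 would report the partial AUC for any subject withdrawn at 1 h or later. A subject in the CHTP-first sequence withdrawn on Day 1 has no mCC tmax, so the item as worded fits an own-product t'. This depends on reading AUC0-t as AUC(0-t').
- Section 5.2 is the only place that names a single product.

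The hints conflict, and Sections 9 and 11.6.2.1 do not resolve them.

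**Step 2: how much does the choice matter?** The SAP has no figure for t', tmax or this ratio, so there is nothing to reproduce. The following is an illustration.

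Inputs from the SAP: nominal sampling times in Table 11; linear trapezoids and linear interpolation (Section 7.1.2).

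Assumptions: linear rise from 0 to Cmax at tmax; decline with a 2-h half-life; mCC and CHTP 1.1 M tmax each 4, 6, 8 or 10 min; Cmax ratio r (CHTP 1.1 M:mCC) of 1.0, 0.7 or 0.5. There are 12 unequal tmax pairs, and 12 × 3 = 36 scenarios.

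Worked case: r = 1, both Cmax scaled to 1, mCC tmax 6 min, CHTP 1.1 M tmax 10 min. Before the peak, AUC(0-t) = t²/(2·tmax); at the peak it is tmax/2.

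- mCC AUC to 6 min: 6/2 = 3.0. CHTP AUC to 6 min: 36/20 = 1.8.
- CHTP AUC to 10 min: 10/2 = 5.0.
- mCC concentration at 8 and 10 min: 2^(−2/120) = 0.9885 and 2^(−4/120) = 0.9772. mCC AUC to 10 min: 3.0 + (1 + 0.9885) + (0.9885 + 0.9772) = 6.954.

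| Reading of t' | CHTP 1.1 M:mCC ratio |
|---|---|
| mCC tmax for both | 1.8/3.0 = 0.60 |
| CHTP 1.1 M tmax for both | 5.0/6.954 = 0.72 |
| Each product's own tmax | 5.0/3.0 = 1.67 |

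**Step 3: the two common cut-offs across the grid.** Changing r multiplies both ratios equally, so the relative gap depends only on the two tmax values. It is the same whichever product peaks later.

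| tmax pair (min) | Rise in ratio, CHTP t' over mCC t' |
|---|---|
| 8 and 10 | 4.4% |
| 6 and 8 | 6.9% |
| 4 and 6 | 12.8% |
| 6 and 10 | 19.8% |
| 4 and 8 | 34.4% |
| 4 and 10 | 58.3% |

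Under these profiles the CHTP cut-off always gives the higher ratio. If CHTP 1.1 M peaks later, the longer window lets it catch up; if it peaks earlier, the shorter window captures its lead. The two readings fall on opposite sides of 1 in 3 of 36 scenarios, for example 0.93 against 1.05 with mCC at 6 min, CHTP 1.1 M at 4 min and r = 0.7.

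**Step 4: own tmax against mCC t'.** These fall on opposite sides of 1 in 19 of 36 scenarios: 12 of 12 at r = 1, 6 of 12 at r = 0.7 and 1 of 12 at r = 0.5. They need not: with mCC at 6 min, CHTP 1.1 M at 10 min and r = 0.5, the ratios are 0.30 (mCC t') and 0.83 (own), both below 1.

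**Step 5: sensitivity.** With a half-life of 1 h or 3 h the counts stay at 3 and 19, and the Step 3 gap runs from 4.6% to 60.3% (1 h) or 4.3% to 57.6% (3 h). All three readings agree when the two tmax values are equal.

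**The case against.** The best reply is that Section 5.2 defines the endpoint, interpolation fits an mCC time applied to the CHTP 1.1 M profile, and no other passage states a different single reference. The analyst would then probably use the mCC tmax, and this is loose drafting. That is a fair prediction, but the operative rule and Table 3 still contradict the objective.

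The objections to the size carry more weight.

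- The most striking figures, 1.67 and 19 of 36, belong to the own-tmax reading, which has the least support. The fairer measure is the gap between the two common cut-offs: 4.4% to 12.8% for adjacent sampling times, with 3 reversals.
- The counts are not probabilities. Adding the 12 equal-tmax cells makes them 3 and 19 of 48.
- Each scenario gives every subject the same pair of tmax values, whereas the endpoint is a geometric mean ratio over subjects. At r = 1, with half the subjects at 6/10 min (mCC/CHTP 1.1 M) and half at 10/6, the ratios are √(0.600 × 1.391) = 0.91 for mCC t', √(0.719 × 1.667) = 1.09 for CHTP t' and √(1.667 × 0.600) = 1.00 for own tmax. The large contrast goes, but the two common cut-offs still differ by 19.8%.

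Item 4 of Section 11.1.5 is also a general list that does not discuss t', and it covers subjects who do have an mCC tmax. It is weak evidence of intent, and the contradiction does not rest on it.

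**Conclusion.** The point stands: a named secondary endpoint has conflicting definitions in current text, and the calculation rule does not identify a single cut-off. In the scenarios examined, choosing between the two common cut-offs moves the ratio by 4.4% to 58.3%, towards the low end when the peaks fall at adjacent sampling times. The own-tmax reading can move it much further and change its direction, but is less likely to be intended. These sizes rest on assumed tmax, half-life, Cmax ratio and profile shape. The contradiction itself rests on the text alone.

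The reach is limited. Cmax, AUC(0-last) and the sample size do not depend on t', no hypothesis is tested (Section 5.4.1), and no claim rests on individual intervals (Section 11.1.7). It should be corrected, but it does not threaten the primary analysis.

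**What to change.** 1. In both Section 4 entries (t' and AUC(0-t')), Table 3 and Section 7.1.2, define t' as the subject's actual tmax after mCC, as in Section 5.2. State that this one time is applied to both product profiles, by linear interpolation. Delete the nasal-spray wording.
2. State that AUC(0-t') is not calculated for a subject without an mCC tmax.
3. In Section 11.1.5 item 4, make reporting of AUC(0-t') after withdrawal at 1 h or later conditional on an mCC tmax being available.

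Items 2 and 3 leave the ratio analysis unchanged, because Section 11.6.2.1 already requires evaluable data on both products; they affect only listings and descriptive summaries.

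The cost is wording in five places and one setting in the PK software, with no new data. Section 3 allows SAP amendments up to database lock, and this one should be made by then.
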